11.1 Demographic Variables

The demographic variables collected in this study include age, sex, race, ethnicity and iris color. Subjects who record more than one race will be grouped into a single category denoted as multi-racial. Demographic variables will be summarized for the ITT and Safety populations, separately.

Age (years) will be summarized, overall and by treatment, using continuous descriptive statistics. Age will also be categorized as follows: <65 years and \geq 65 years. Age will be reported in years and calculated using the following formula:

$$\text{Age} = (\text{informed consent date} - \text{date of birth}) / 365.25 \text{ truncated as an integer.}$$

The number and percentage of subjects will be presented, overall and by treatment, for age category, sex, race, ethnicity and iris color for each eye separately.

A subject listing that includes all demographic variables will be provided.

11.2 Pretreatment Variables

At Visit 1, subjects signing the informed consent and Health Insurance Portability and Accountability Act (HIPAA) forms will be given a diagnostic test for allergic disease (skin test). Results from this test will be provided in a subject listing.

12. Medical History and Concomitant Medications

12.1 Medical History

Medical history will be coded using Medical Dictionary for Regulatory Activities (MedDRA) 19.1.

Non-ocular medical history will be summarized using discrete summary statistics and presented by treatment group at the subject and event level by System Organ Class (SOC) and Preferred Term (PT) using the ITT population. Ocular medical history will be similarly summarized at the subject level. If a subject reports the same PT multiple times within the same SOC, that PT will only be reported once within that SOC. As with the PT, if a subject reports multiple conditions within the same SOC, that SOC will only be reported once.

Listings of medical history will be generated separately for ocular and non-ocular data.

12.2 Prior and Concomitant Medications

A series of horizontal black bars of varying lengths, likely representing a redacted list of items. The bars are arranged vertically, with the longest bar at the top and the shortest at the bottom. There are several shorter bars interspersed between the longer ones, creating a pattern of alternating lengths.

13. Exposure to Investigational Product

The number and percentage of subjects instilled with IP will be summarized by visit and treatment group for the Safety population. Percentages will be calculated based on the total number of subjects in each treatment group with responses.

A listing of IP instillation for all subjects will also be provided.

14. Efficacy Analyses

14.1 Primary Analysis

The primary efficacy variable is ocular itching evaluated by the subject at 10(±1), 15(±1), and 20(±1) minutes post-CAC measured at Visit 3 (1 hour post treatment) and Visit 4 (10-minutes post treatment).

Ocular itching will be evaluated using the following Ora Calibra™ Conjunctival Allergen Challenge Ocular Itching Scale:

[figure not shown]
[figure not shown]
Term	Percentage
GDP	95
Inflation	92
Interest rates	78
Central bank	75
Monetary policy	72
Quantitative easing	68
Inflation targeting	65
Interest rate hike	62

11. **What is the primary purpose of the following statement?**

10. *Journal of the American Statistical Association*, 1980, 75, 338-342.

the first time in the history of the world, the people of the United States have been called upon to determine whether they will submit to the law of force, or the law of the Constitution. We shall not shrink from that great responsibility. We shall meet the emergency in the spirit of the Constitution, and in accordance with the principles of justice and freedom.

[figure not shown]
1. **What is the primary purpose of the study?** The study aims to evaluate the effectiveness of a new treatment for hypertension in a diverse population.

14.2.1 Ocular Itching

Ocular itching will be evaluated by the subject (0 to 4 scale, with half unit increments) at 5(± 1), 30(± 1) and 60(± 5) minutes post-CAC at Visits 3 and 4 using the same Ora Calibra™ Conjunctival Allergen Challenge Ocular Itching Scale as the primary efficacy analysis. Ocular itching for these time points will be analyzed in a similar manner to ocular itching at the primary analysis time points as described at the beginning of Section 14.2.

Similar analyses will be conducted for subgroups defined by gender, age, allergen and baseline itching scores.

[REDACTED]

[REDACTED]

[REDACTED]

[REDACTED]

[REDACTED]

[REDACTED]

[REDACTED]

15. Exploratory Analyses

There is no planned exploratory analysis for this study.

16. Safety Analyses

The primary safety variable is the incidence of subjects with any AE during the entire study.

The secondary safety variables of visual acuity, slit-lamp biomicroscopy, IOP and dilated fundus examination will be summarized descriptively using quantitative and qualitative summary statistics as appropriate. Changes and shifts from baseline will also be summarized where applicable.

All safety analyses will be conducted using the Safety Population. No statistical inferential testing will be performed for safety variables.

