
Ocular itching evaluated by the subject at 10(±1), 15(±1), and 20(±1) minutes post-CAC at Visits 3 and 4 (0-4 scale, allowing half unit increments)

Sponsor: Aldeyra Therapeutics, Inc.

Name of Finished Product: ADX-102

Name of Active Ingredient: ADX-102 Ophthalmic Drops (0.5%) and ADX-102 Ophthalmic Drops (0.1%)

Protocol Title: A Multi-Center, Double-Masked, Randomized, Vehicle-Controlled, Phase 2b Evaluation of the Onset and Duration of ADX-102 Ophthalmic Drops (0.5% and 0.1%) Compared to Vehicle of ADX-102 Ophthalmic Drops in the Conjunctival Allergen Challenge (Ora-CAC®) Model of Acute Allergic Conjunctivitis

Safety Measures:

- Adverse Events (reported, elicited and observed)
- Visual Acuity at Distance Utilizing an ETDRS chart
- Slit-lamp Biomicroscopy
- Intraocular Pressure
- Dilated Fundoscopy

General Statistical Methods and Types of Analyses

Approximately 150 subjects will be randomized at Visit 3, or approximately 50 subjects per treatment arm.

Quantitative variables will be summarized using descriptive statistics, that is, number of observations, mean, standard deviation, median, minimum, and maximum. Qualitative variables will be summarized using counts and percentages. Statistical testing will be performed at a two-sided significance level of alpha = 0.05. For all analyses, comparisons will be made between each dose of ADX-102 Ophthalmic Drops and vehicle.

[figure not shown]
[figure not shown]
[figure not shown]

Sponsor: Aldeyra Therapeutics, Inc.

Name of Finished Product: ADX-102

Name of Active Ingredient: ADX-102 Ophthalmic Drops (0.5%) and ADX-102 Ophthalmic Drops (0.1%)

Protocol Title: A Multi-Center, Double-Masked, Randomized, Vehicle-Controlled, Phase 2b Evaluation of the Onset and Duration of ADX-102 Ophthalmic Drops (0.5% and 0.1%) Compared to Vehicle of ADX-102 Ophthalmic Drops in the Conjunctival Allergen Challenge (Ora-CAC®) Model of Acute Allergic Conjunctivitis

The primary efficacy variable is measured at Visit 3 (1 hour post treatment) and Visit 4 (10 minutes post treatment).
   

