12.4 CRITERIA FOR EFFICACY

This clinical study is designed to evaluate the efficacy of ADX-102 Ophthalmic Drops compared to vehicle in the prevention of ocular itching at each designated time point post-CAC at Visits 3 and 4.

[figure not shown]
To demonstrate the clinical effectiveness for ocular itching, ADX-102 Ophthalmic Drops will need to show clinical superiority over vehicle by at least 0.5 units of a 5 point scale for the 10(± 1), 15(± 1) and 20(± 1) minutes post-CAC time points within a visit, and at least 1 unit for the majority [REDACTED] of the same three post-CAC time points within a visit for each treatment comparison. ADX-102 Ophthalmic Drops will also need to show statistical superiority over vehicle at each of the three time points. The treatments will be tested against vehicle hierarchically, with the higher dose (0.5% ADX-102 Ophthalmic Drops) tested first and the lower dose (0.1% ADX-102 Ophthalmic Drops) tested conditional upon the higher dose showing statistical significance over vehicle.

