5.1 Method of Assigning Subjects to Treatment Groups

All subjects screened for the study who sign an ICF will be assigned a 3-digit screening number that will be entered in the Screening and Enrollment Log. Screening numbers will be assigned in a sequential order beginning with 001. Randomization will be used to avoid bias in the assignment of subjects to treatment and time point, to increase the likelihood that known and unknown subject attributes (e.g., demographics and baseline characteristics) are evenly balanced across treatment groups and across time points, and to enhance the validity of statistical comparisons.

Once a subject meets all qualification criteria at Visit 3 (Day 1), they will be enrolled and randomly assigned to masked treatment using a 1:1:1 (ADX-102 ophthalmic drops [0.1%]: ADX-102 ophthalmic drops [0.5%]: vehicle of ADX-102 ophthalmic drops) assignment ratio. Subjects will be assigned the lowest 4-digit randomization number available at the Investigative site within the appropriate stratum. The randomization number will be stratified by the average post-CAC itching scores [REDACTED] at baseline (Visit 2) to ensure balance for the primary endpoint of ocular itching. No randomization numbers will be skipped or omitted.

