9.4 Data Analysis Conventions

All data analysis will be performed by SDC after the study is completed and the database has been locked and released for unmasking. Statistical programming and analyses will be performed using SAS[®] Version 9.4 or higher. Output will be provided in rich text format (RTF) for tables and portable document format (PDF) for tables, listings, and figures using landscape orientation. All study data will be listed by subject, treatment, visit and time point (as applicable) based on all randomized subjects unless otherwise specified.

Summaries for quantitative variables will include the number of observations (n), arithmetic mean, standard deviation (SD), median, minimum, and maximum. Minima and maxima will be reported with the same precision as the raw values; means and medians will be presented to one additional decimal place than reported in the raw values. Standard deviations will be presented to two additional decimal places than reported in the raw values. Summaries for qualitative variables will include frequency counts and percentages. All percentages will be rounded to one decimal place (i.e., XX.X%). Differences between active treatment groups and placebo will be calculated as active minus vehicle and change from baseline will be calculated as follow-up visit minus baseline visit.

All statistical tests will be two-sided with a significance level of 0.05 ($\alpha = 0.05$) unless otherwise specified. Confidence intervals (CI) for differences between treatment groups will be two-sided at 95% confidence. All p-values will be rounded to four decimal places; p-values less than 0.0001 will be presented as "<0.0001"; p-values greater than 0.9999 will be presented as ">0.9999".

Unless otherwise specified, summaries will be presented by treatment group and, where appropriate, visit and time point.

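### Do the planned subgroup analyses of ocular itching lack an interaction test or a rule for reading them?

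*SAP*

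**What the plan says.** SAP 14.2.1 deals with itching at 5, 30 and 60 "minutes post-CAC at Visits 3 and 4 using the same Ora Calibra™ Conjunctival Allergen Challenge Ocular Itching Scale as the primary efficacy analysis". For the method it refers back: these time points are handled like the primary ones, "as described at the beginning of Section 14.2". The subgroup sentence follows: "Similar analyses will be conducted for subgroups defined by gender, age, allergen and baseline itching scores".

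The general conventions in SAP 9.4 add two things. The first is a default level: "All statistical tests will be two-sided with a significance level of 0.05", which the same sentence lets other text override. The second is a convention for estimates: "Confidence intervals (CI) for differences between treatment groups will be two-sided at 95% confidence".

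The criteria for success are in Protocol 12.4. They require "clinical superiority over vehicle by at least 0.5 units of a 5 point scale" at the 10, 15 and 20 minute time points, at least 1 unit at most of those time points, and statistical superiority at each. The 0.5% dose is tested first and the 0.1% dose only if the first succeeds. Subgroups do not appear there.

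Several places cannot be read in the public copy: most of SAP 14.1, the opening of 14.2, the text after the subgroup sentence (seven redacted blocks), the body of 9.5 on multiplicity, and the contents of the table, listing and figure lists in Sections 20 to 22.

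**The concern.** Four factors are named (gender, age, allergen, baseline itching), and the analyses are to be similar to those for the whole trial. Read with the default 0.05 level, this suggests a p-value in each subgroup. A significant result in one subgroup beside a non-significant result in another is easily taken as a difference in effect. It is not a test of one: the contrast can come entirely from the smaller numbers in one subgroup. The usual safeguards are an interaction test, estimates with confidence intervals, or a statement that the output is descriptive, and only the confidence-interval convention is in view.

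Two other readable statements sharpen the suspicion. SAP 15 says no exploratory analysis is planned, so no exploratory label visibly covers the subgroups. SAP 16 rules out inferential testing for safety, and no readable sentence does the same for subgroups. If the suspicion were right, the study report could describe ADX-102 as working in, say, one sex or one allergen group on chance alone.

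**Working it through.** **Inputs from the documents.** Sample size (Protocol synopsis): "Approximately 150 subjects will be randomized at Visit 3, or approximately 50 subjects per treatment arm", and 150 / 3 = 50 agrees with the 1:1:1 ratio in SAP 5.1. Two-sided level 0.05 (SAP 9.4). Effects of 0.5 and 1 unit, the two thresholds in Protocol 12.4.

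**Assumed, because the public copy does not show them.** SD 0.8 to 1.3 units; subgroup splits of 25:25, 40:10 and 45:5 per arm; no dropout; one dose against vehicle at one time point; a t-test in each subgroup.

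**Step 1: how often identical effects look different.** With n per arm in a subgroup, power comes from the noncentral t distribution with 2n − 2 degrees of freedom and noncentrality effect / (SD × √(2/n)). If a and b are the powers in the two subgroups, exactly one is significant with probability a(1 − b) + b(1 − a).

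Example: 25 per arm, effect 0.5, SD 1.0. Noncentrality = 0.5 / √(2/25) = 1.77; power 0.410; probability = 2 × 0.410 × 0.590 = 0.484.

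| Split per arm | Effect | SD 0.8 | SD 1.0 | SD 1.2 | SD 1.3 |
|---|---|---|---|---|---|
| 25:25 | 0.5 | 49% | 48% | 42% | 39% |
| 25:25 | 1.0 | 2% | 12% | 29% | 37% |
| 40:10 | 0.5 | 64% | 56% | 47% | 42% |
| 40:10 | 1.0 | 25% | 44% | 57% | 61% |
| 45:5 | 0.5 | 74% | 62% | 50% | 45% |
| 45:5 | 1.0 | 59% | 71% | 77% | 78% |

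The general warning is therefore sound. The range, 2% to 78%, is set by the assumptions; no readable passage gives an SD or a subgroup size, and the top end needs a subgroup of five subjects per arm.

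**Step 2: how an interaction test would do.** With equal halves, the standard error of the difference between the two subgroup effects is SD × √(2/25 + 2/25) = 0.4 × SD, that is 0.32, 0.40, 0.48 and 0.52 at the four SDs. Normal-approximation power for a true 0.5-unit difference in effect is 35%, 24%, 18% and 16%; for a 1-unit difference it is 88%, 70%, 55% and 49%. The false-positive rate is 5% per test if the SD is common to the subgroups. With a 45:5 split, a pooled-variance interaction test and no true effect, simulation gives about 5% at equal SDs, about 18% if the small subgroup has SD 1.3 and the large one 0.8, and about 0.5% in the reverse case. One such test per factor, dose, visit and time point makes 4 × 2 × 2 × 3 = 48 tests and 48 × 0.05 = 2.4 expected false positives when there is nothing to find. An interaction test is the right tool for the question, but it would not settle much in a trial of this size.

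**Step 3: does the plan do what Step 1 warns against?** Three things would all have to be true.

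1. *The plan has no interaction test, reading rule or descriptive label.* This cannot be concluded. SAP 14.2.1 takes its method from the opening of 14.2, which is not readable, and the text after the subgroup sentence is blacked out. These are the natural places for such a rule.
2. *Within-subgroup p-values will be produced.* This is not established. SAP 9.4 sets the level for tests that are done; it does not order a test in each subgroup. The same section makes 95% intervals for treatment differences the convention.
3. *Those p-values will be contrasted and read as a difference in effect.* No readable sentence plans this.

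**Step 4: does anything depend on it?** The criteria and dose hierarchy in Protocol 12.4 use the comparison of each dose with vehicle only. Whatever the subgroup tables show, they cannot change whether the trial meets its criteria.

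**The case for a change.** The best case for the concern is that it can be put conditionally: if the hidden text has no rule, then one is needed. The visible contrast with the safety section, where inferential testing is expressly excluded, gives that some weight. The misreading is also common: with two levels per factor there would be 4 × 2 levels × 2 doses × 2 visits × 3 time points = 96 subgroup comparisons, so some discordant pairs would be likely if p-values were shown. The remedy would be cheap: one model term per factor and a descriptive label.

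What stands is the statistical principle and the arithmetic in Step 1. Anyone reading the eventual subgroup tables should look at the differences and their intervals, not at which ones cross 0.05. What does not stand is the step from there to a defect. A conditional criticism whose condition lies under redaction is a question about the unredacted document. The safety sentence does not help, because the corresponding statement for subgroups could be in the blacked-out lines of 14.2. The statement in SAP 15 is also weak evidence: the subgroup analyses sit under 14.2, so their status would be described there.

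**Conclusion.** The concern does not hold. An interaction test and a reading rule are not visible, but the places where they would stand are redacted or illegible, and text withheld from the public copy is not missing from the plan. The harm also requires that subgroup p-values are produced and then contrasted, neither of which the readable text plans. Even then it would touch interpretation only, since subgroups have no part in the success criteria.

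The rates of apparent disagreement (39% to 49% for a 0.5-unit effect and 2% to 37% for a 1-unit effect in equal halves) are correct under 50 per arm, an assumed SD of 0.8 to 1.3 and t-tests within subgroups. They describe a general hazard of comparing p-values, not a procedure found in this plan. An interaction test would have only 16% to 35% power for a 0.5-unit difference in effect, so its presence or absence would change little in what this phase 2b trial can say about subgroups. This conclusion rests on the public copy; it does not assert that the hidden text contains a rule.

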16.1 Adverse Events

An AE is defined as any untoward medical occurrence associated with the use of an IP in humans, whether or not considered IP-related. An AE can be any unfavorable and unintended sign (e.g., an abnormal laboratory finding), symptom, or disease temporally associated with the use of an IP, without any judgment about causality. An AE can arise from any use of the IP (e.g., off-label use, use in combination with another drug or medical device) and from any route of administration, formulation, or dose, including an overdose. An AE can arise from any delivery, implantation, or use of a medical device, including medical device failure, subject characteristics that may impact medical device performance (e.g., anatomical limitations), and therapeutic parameters (e.g., energy applied, sizing, dose release) associated with medical device.

All AEs spontaneously reported by the subject and/or in response to an open question from study personnel or revealed by observation, physical examination or other diagnostic procedures will be recorded in the source document and on the appropriate pages of the eCRF. Any clinically relevant deterioration in clinical finding is considered an AE and must be recorded. When possible, signs and symptoms indicating a common underlying pathology should be noted as one comprehensive event. Any pre-existing medical condition that worsens after administration of study medication will also be considered a new AE. Study medication includes the drug under evaluation or any other medications required by the protocol given during any stage of the study.

Ocular complaints should not be addressed as AEs unless the complaint is outside the normal limits for allergic conjunctivitis symptoms after allergen exposure or is associated with clinical sequelae (i.e., adverse slit-lamp examination finding).

Treatment-emergent adverse events (TEAEs) are defined as any event that occurs or worsens on or after the day that randomized study treatment is initiated.

An AE is considered serious if, in the view of either the investigator or sponsor, it results in any of the following outcomes:

- Death;
- A life-threatening AE;

Note: An AE is considered “life-threatening” if, in the view of either the investigator or Sponsor/designee, its occurrence places the subject at immediate risk of death. It does not include an AE that, had it occurred in a more severe form, might have caused death.

- Inpatient hospitalization or prolongation of existing hospitalization;

Note: The term “inpatient hospitalization” refers to any inpatient admission (even if less than 24 hours). For chronic or long-term inpatients, inpatient admission includes transfer within the hospital to an acute/intensive care inpatient unit. Inpatient hospitalization does not include: emergency room visits; outpatient/same-day/ambulatory procedures; observation/short stay units; rehabilitation facilities; hospice facilities; nursing homes; or clinical research/phase 1 units.

Note: The term “prolongation of existing hospitalization” refers to any extension of an inpatient hospitalization beyond the stay anticipated or required for the reason for the initial admission as determined by the investigator or treating physician.

- A persistent or significant incapacity or substantial disruption of the ability to conduct normal life functions;

Note: A SAE specifically related to visual threat would be interpreted as any potential impairment or damage to the subject’s eyes (e.g., hemorrhage, retinal detachment, central corneal ulcer or damage to the optic nerve).

- A congenital anomaly/birth defect.

Important medical events that may not result in death, are life-threatening, or require hospitalization may be considered serious when, based upon appropriate medical judgment, they may jeopardize the subject and may require medical or surgical intervention to prevent one of the outcomes listed in this definition.

The relationship of each AE to the IP should be determined by the investigator using these explanations:

- *Suspected*: A reasonable possibility exists that the IP caused the AE.
- *Not Suspected*: A reasonable possibility does not exist that the IP caused the AE.

Note: "Reasonable possibility" means there is evidence to suggest a causal relationship between the investigational product and the AE. Types of evidence that would suggest a causal relationship between the investigational product and the AE include: a single occurrence of an event that is uncommon and known to be strongly associated with investigational product exposure (e.g., angioedema, hepatic injury, Stevens-Johnson Syndrome); one or more occurrences of an event that is not commonly associated with investigational product exposure, but is otherwise uncommon in the population exposed to the investigational product (e.g., tendon rupture); an aggregate analysis of specific events observed in a clinical trial (such as known consequences of the underlying disease or condition under investigation or other events that commonly occur in the study population independent of drug therapy) that indicates those events occur more frequently in the investigational product-treatment group than in a concurrent or historical control group.

Severity of an AE is defined as a qualitative assessment of the degree of intensity of an AE as determined by the investigator or reported to him/her by the subject. The assessment of severity is made irrespective of relationship to IP or seriousness of the event and should be evaluated according to the following scale:

- *Mild*: Event is noticeable to the subject, but is easily tolerated and does not interfere with the subject's daily activities.
- *Moderate*: Event is bothersome, possibly requiring additional therapy, and may interfere with the subject's daily activities.
- *Severe*: Event is intolerable, necessitates additional therapy or alteration of therapy, and interferes with the subject's daily activities.

An overall summary will be presented that includes the number of AEs and the number and percentage of subjects who experienced at least one AE, by treatment group and for all subjects combined. This summary will also include breakdowns of AEs further categorized as ocular or non-ocular, SAEs, AEs by maximum severity and relationship to IP, number of subjects with AEs leading to subject withdrawal and number of subjects with AEs resulting in death. TEAEs summarized for the same categories will also be included.

Additional summaries of AEs will be provided showing the number of AEs and the number and percentage of subjects who experienced at least one AE. These summaries will be presented at the subject and event level by SOC and PT. If a subject reports the same PT multiple times within the same SOC, that PT will only be reported once within that SOC. As with the PT, if a subject reports multiple conditions within the same SOC, that SOC will only be reported once. In the summary, SOC will be listed in ascending alphabetical order; PTs will be listed in order of descending frequency for all subjects within each SOC. These summaries will be presented for ocular and non-ocular AEs separately and include the following:

- All AEs;
- All TEAEs;
- All TEAEs suspected to be related to the IP;
- All SAEs;
- All TEAEs by maximal severity; and

Subject listings will be provided for all adverse events, serious adverse events, adverse events leading to death and adverse events leading to study treatment discontinuation.

